#### **4.4. Efficacy Analyses**

The mITT population will be the primary population for the analysis of all efficacy endpoints. All efficacy endpoints will also be analyzed with the ITT and PP populations. Subjects will be analyzed according to their randomized treatment group.

All BMD-related endpoints will be derived from the Calyx-corrected BMD measurements.

BMD scans may be deemed unevaluable at the first reading and a repeat BMD scan may be performed. The re-scan BMD assessment will be recorded as an unscheduled visit for the corresponding nominal visit. To determine the assessment that will be used for a given study visit by the analysis window convention, all BMD assessments (including unscheduled BMD assessments) will be considered. In the efficacy analyses by nominal visit, unscheduled BMD assessments will be used if the BMD assessment at the nominal visit is not available but an unscheduled BMD assessment for the same nominal visit is available.

Analyses of the BMD-related efficacy endpoints and the serum markers of bone metabolism (s-PINP and s-CTX) will be conducted using the analysis visit windows defined in [Table 3](#) of [Section 3.12](#) as the primary analysis. Analyses of the BMD-related efficacy endpoints and the serum markers of bone metabolism (s-PINP and s-CTX) using the nominal visits will also be presented as supportive analyses. Study sites collected samples for bone turnover marker assessment in 4 aliquots per subject at each collection timepoint. When more than 1 aliquot was analyzed for a given timepoint for a subject, the average of the results for that timepoint for that subject will be used in the analysis.

Unless otherwise specified, all CIs, statistical tests, and p-values will be reported as nominal 2-sided from testing for treatment difference, with a significance level of 0.05.

##### **4.4.1. Primary Efficacy Endpoint**

###### **4.4.1.1. Primary Analysis**

The primary efficacy endpoint is the percent change from baseline in lumbar spine BMD at 12 months.

The primary hypothesis is that the effect of abaloparatide-sMTS 300 µg worn 5 minutes on the thigh on the percent change from baseline in lumbar spine BMD at 12 months is no worse than the effect of abaloparatide-SC 80 µg by a non-inferiority margin of 2.0%. Non-inferiority of

abaloparatide-sMTS to abaloparatide-SC will be concluded if the lower bound of the 2-sided 95% CI for the estimated treatment difference (abaloparatide-sMTS minus abaloparatide-SC) in the percent change from baseline in lumbar spine BMD at 12 months is above -2.0%, using an MMRM analysis.

The primary efficacy endpoint will be analyzed using an MMRM with fixed effects of treatment, DXA instrument manufacturer, visit, and treatment-by-visit interaction, and with baseline lumbar spine BMD as a covariate. Imputation for missing data is not necessary for the MMRM model because the model uses a restricted maximum likelihood (REML) based on the repeated-measures approach. An unstructured variance-covariance matrix will be used to model the within- and between-subject variabilities over the visits. The Kenward-Roger approximation will be used to estimate denominator degrees of freedom and to adjust standard errors ([Kenward and Roger, 1997](#)). Analyses will be implemented using the SAS PROC MIXED procedure. The least square (LS) means for the treatment groups and LS means and corresponding 95% CIs for the treatment differences (abaloparatide-sMTS minus abaloparatide-SC) at Month 12 will be derived from the MMRM model.

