6.2.7. Treatment Period

Subjects who remain eligible for study participation will be randomly allocated to a treatment group through the IRT, using a 1:1 randomization ratio on Day 1 to receive treatment with either abaloparatide-SC 80 μ g per day or daily 300 μ g abaloparatide-sMTS administration. During the Treatment Period, subjects will self-administer a single dose of study drug once a day. Subjects will also take calcium and vitamin D each day during the Treatment Period, as directed by the Investigator.

Subjects will be randomized on Day 1 of the Treatment Period. During the Treatment Period, subjects will self-administer study drug once a day for 12 months and visit the study site as shown in Table 1.

At each study site visit during this period, as indicated in Table 1, recent health status will be obtained, the diary reviewed, AEs collected, and orthostatic blood pressure and vital signs performed. Laboratory assessments of chemistry, hematology, and urinalysis will be obtained at Day 1, Month 1, Month 6, and Month 12 and a 24-hour urine collection will start on the day prior to Day 1 and on the day prior to the Month 3 visit. Clinical assessments for fracture will be performed at the pretreatment visit and at Day 1 and Months 1, 3, 6, 9, and 12. Source documentation (imaging report and/or film along with other supporting documentation as appropriate) will be collected from each site to confirm fracture.

Subjects will have BMD assessed by DXA at the lumbar spine, total hip, and femoral neck at Screening and Months 3, 6, and 12. All DXA assessments will be performed by a central imaging laboratory. Bone turnover marker assessments (s-PINP and s-CTX) will be performed on Day 1 and Months 1, 3, 6, and 12.

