8.4.2. Analysis of the Primary Efficacy Endpoint(s)

The primary hypothesis is that the effect of abaloparatide-sMTS 300 µg worn 5 minutes on the thigh on the percent change from baseline in lumbar spine BMD at 12 months is no worse than the effect of abaloparatide-SC 80 µg by a non-inferiority margin of 2.0%. The primary efficacy endpoint will be analyzed using an Mixed-Effect Model Repeated Measures (MMRM) model with fixed effects of treatment, DXA instrument manufacturer, visit, and treatment-by-visit interaction and with baseline lumbar spine BMD as covariate. An unstructured variance-covariance matrix will be used to model the within-subject errors over the visits. The estimated difference (abaloparatide-sMTS minus abaloparatide-SC) and its corresponding 2-sided 95% confidence interval (CI) will be derived from the MMRM model. If the lower bound of the 2-sided 95% CI for the between-group difference in mean percent change from baseline in lumbar spine BMD at 12 months is above -2.0%, non-inferiority of abaloparatide-sMTS to abaloparatide-SC will be concluded.

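### The primary MMRM has no baseline-by-visit term; adding it costs 2 df and would make the Month 12 contrast slightly more robust and precise if baseline slopes differ by visit

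*SAP*

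**What the plan says.** SAP 4.4.1.1 specifies "fixed effects of treatment, DXA instrument manufacturer, visit, and treatment-by-visit interaction", "and with baseline lumbar spine BMD as a covariate". Protocol 8.4.2 gives the same model: "with fixed effects of treatment, DXA instrument manufacturer, visit, and treatment-by-visit interaction and with baseline lumbar spine BMD as covariate". Neither lists an interaction of baseline with visit.

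Three post-baseline scans enter the model: "Subjects will have BMD assessed by DXA at the lumbar spine, total hip, and femoral neck at Screening and Months 3, 6, and 12". The covariance is left free: "An unstructured variance-covariance matrix will be used to model the within- and between-subject variabilities over the visits". The decision uses Month 12 only, through the "lower bound of the 2-sided 95% CI for the estimated treatment difference" compared with -2.0%.

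No MMRM in SAP 4.4.1.2 adds the term. The ITT and PP repeats, the tipping-point analysis and the COVID-19 window analyses all keep the primary model's covariates. The washout and LOCF ANCOVAs fit Month 12 alone, so their baseline slope is specific to that visit. Neither document gives a reason for the common slope.

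**The concern.** The outcome is percent change, so baseline BMD is in its denominator. If the absolute gain is unrelated to baseline, women with low baseline BMD show larger percent gains, and the slope on baseline grows as the mean gain builds over the year. A slope pooled over three visits would then be too shallow at Month 12.

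Two things follow. Baseline variation at Month 12 is only partly removed, so the interval is slightly wider than it need be. And part of any chance difference in baseline BMD between arms stays in the estimate. Randomisation is described only as permuted block, with no stratification by baseline BMD stated, so covariate adjustment is the protection the plan describes. The design has little reserve, since its power is close to 90% at the planned size.

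**Working it through.** **The plan's own figure.** Inputs from SAP 3.1: margin 2.0, SD 6.35, true difference 0, 2-sided 95% CI, at least 90% power. With 213 per arm the SE is 6.35 × √(2/213) = 0.615 and the half-width is 1.96 × 0.615 = 1.21. Noncentral-t power is 0.9003 (0.8989 with 212 per arm), so 426 is reproduced. 426/0.90 = 473.3, or 474 when rounded up to equal arms.

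**Is a growing slope plausible?** If absolute gain is unrelated to baseline, the correlation of baseline with percent change is about -(mean % gain × baseline CV)/SD. I take the placebo-adjusted 12-month effect of 9.096% (SAP 3.1) as a stand-in for the gain, and assume a baseline CV of 10-15%, which the documents do not give. This yields -(9.096 × 0.10)/6.35 = -0.14 to -(9.096 × 0.15)/6.35 = -0.21 at Month 12, and less at earlier visits, where the gain is smaller.

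**Large-sample comparison (complete data).** Let b_t be the slope per baseline SD at visit t (correlation × SD at that visit), b_c the generalised-least-squares pooled slope, and d = b_12 - b_c. Then:

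- Month 12 residual variance is S = 6.35² × (1 - r²) with the interaction and S + d² without it, so the variance excess is d²/S.
- The shift per 1-SE baseline imbalance is |d| × √(2/213) = |d| × 0.0969.

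Worked cases, with assumed SDs of 4, 5 and 6.35 and between-visit correlation 0.6:

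| Correlations at Months 3/6/12 | Slopes b_t | b_c | d | S | d²/S | Shift per 1 SE |
|---|---|---|---|---|---|---|
| -0.20/-0.20/-0.20 | -0.80/-1.00/-1.27 | -0.84 | -0.43 | 38.7 | 0.5% | 0.04 |
| -0.05/-0.10/-0.20 | -0.20/-0.50/-1.27 | -0.24 | -1.03 | 38.7 | 2.8% | 0.10 |
| -0.10/-0.20/-0.30 | -0.40/-1.00/-1.91 | -0.53 | -1.38 | 36.7 | 5.2% | 0.13 |

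**Range.** The SDs were varied between 3.5/4.8/6.35 and 5/5.7/6.35, and the between-visit correlation between 0.5 and 0.7:

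- Constant correlation of -0.1 to -0.3: variance excess about 0.03-2.4% (the smallest corner rounds to 0.02%), shift 0.01-0.09 points per 1 SE. Since √1.024 = 1.012, the interval is at most about 1.2% wider.
- Steep growth (the last two rows of the table): excess about 1.5-8%, shift 0.07-0.17 points. Since √1.015 = 1.007 and √1.08 = 1.039, the interval is about 0.7-3.9% wider.

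**Simulation of both models by REML.** About 12% of Month 12 values were missing, with 500-600 trials per scenario. The manufacturer effect was left out, and a fixed t value replaced Kenward-Roger.

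| Scenario | Mean SE, planned | Mean SE, with interaction | Correlation of estimate with imbalance |
|---|---|---|---|
| Equal slopes (zero) | 0.6415 | 0.6422 | -0.01 → -0.01 |
| Slopes in ratio 0.35/0.65/1, r = -0.2 | 0.634 | 0.630 | -0.14 → -0.01 |
| Slopes in ratio 0.35/0.65/1, r = -0.3 | 0.624 | 0.614 | -0.20 → -0.01 |

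With equal slopes the interaction model was tighter in only about 20% of trials. In every scenario the planned model's mean estimate was within about 0.03 of the truth and its coverage was 94.5-95.0%. False non-inferiority at a true difference of -2 was 1.4-1.8%, with a Monte Carlo error of about 0.7 points.

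**The case against.** The strongest reply is that this is a choice between two valid prespecified models. Nothing in the documents shows that the slopes differ, and if they do not, the extra term gains nothing. That stands: the benefit is conditional, and the figures above depend on assumed inputs. With the milder pattern, a constant correlation, the effect can be negligible. The 3-5% excess in the lower rows of the first table comes from slopes that grow about five- or six-fold between Months 3 and 12.

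A reader might infer that the common slope biases the primary result or inflates the risk of a false non-inferiority claim. The model does not imply that. Allocation is 1:1 at random, so the dependence on imbalance averages to zero and can favour either arm. The unstructured covariance absorbs the slope misfit into the residual variance, so the interval keeps its coverage. A reader might also infer that the extra term always tightens the interval; with equal slopes it does not.

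The single-visit ANCOVAs already carry a Month 12 slope, and a material discrepancy with the MMRM could show up there. This helps only in part, because they handle missing data differently and a discrepancy could not be attributed to the slope.

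**Conclusion.** The point holds as a refinement. The primary model imposes a restriction that the plan does not justify, at the one visit that matters, and relaxing it costs 2 parameters in about 426 subjects. Under the assumed inputs the effect runs from nothing (equal slopes) to about 8% of Month 12 variance and 0.17 points per 1-SE imbalance (steepest growth considered), against a margin of 2.0. Milder growth gives at most 2.4% and 0.09 points. The baseline correlations, the Month 3 and 6 SDs and the between-visit correlations are all assumptions. The planned analysis remains valid without the change.

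**What to change.** Add a baseline lumbar spine BMD-by-visit interaction to the primary MMRM in SAP 4.4.1.1, and carry it into the MMRM-based sensitivity analyses. For consistency, use the matching term in the total hip and femoral neck models (2 df each) and in the turnover-marker models (3 df, since markers are measured at Months 1, 3, 6 and 12). The gain was calculated for lumbar spine only.

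The cost is 2 df in the primary model and, if slopes are equal, an SE about 0.1% larger. Because the protocol states the model without the term, the change is a departure to be listed in SAP section 5 and fixed before database lock. SAP 1.2.3 says the sponsor receives no post-baseline BMD until lock, so a change made before then would not be driven by the results.

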#### **4.4.1.2. Sensitivity Analysis**

The primary analysis using the MMRM model for the primary efficacy endpoint will be repeated using the ITT and PP populations to support the finding from the mITT population. Additional sensitivity analyses described below will also be performed in the mITT, ITT, and PP populations.

The primary analysis using MMRM model is based on the missing at random (MAR) assumption. To assess the impact of deviations from the MAR assumption for the primary analysis, a sensitivity analysis using the tipping-point approach will be conducted on the primary efficacy endpoint to assess the robustness of the primary analysis result.

The tipping point approach assesses how severe departures from MAR must be to overturn conclusions from the primary analysis. If implausible departures from MAR to change the results from being favorable to the experimental treatment to being unfavorable, the results will be said to be robust to the departure from MAR assumption. This provides additional confidence in the results obtained based on the MMRM model with the MAR assumption.

The tipping point analysis will only be performed if NI is concluded based on the primary analysis using MMRM.

Implementation of the tipping point analysis requires performing multiple imputation of missing lumbar spine BMD data under the missing not at random (MNAR) assumption with a sequence of shift parameters, which adjust the imputed values for the abaloparatide-sMTS treatment group.

Implementing the tipping point analysis include the following steps with the first three steps being the standard multiple imputation (MI) steps:

1. The missing data in both arms will be imputed 100 times to generate 100 complete data sets. The following process will be followed within Step 1:
  - a) A seed value of 940938 will be used in SAS PROC MI.

- b) The Markov Chain Monte Carlo (MCMC) method will be used to impute the intermediate missing values, so that the missing values follow a monotone pattern. One hundred data sets will be generated.
- c) For each of the 100 generated data sets, the monotone missing values will be imputed using the pattern-mixture model approach with a regression method. At this step, a shift parameter of zero will be applied. The SAS PROC MI methodology with the MNAR statement for imputation of monotone missing data patterns will be used in this step.

2. Percent changes from baseline will be calculated and each of the 100 complete data sets will be analyzed using the MMRM model as described in [Section 4.4.1.1](#).
3. The results from the 100 complete data sets will be combined for the statistical inference using SAS PROC MIANALYZE.
4. The imputation at Step 1 above will start with 0 shift in both arms. If the lower bound of the 95% CI for the difference between abaloparatide-sMTS and abaloparatide-SC at Step 3 is greater than -2.0%, repeat Step 1c) to generate multiple imputed data sets, with a specified non-zero shift parameter that adjusts the imputed values in the abaloparatide-sMTS group. Otherwise, no further imputation will be performed, and it will be concluded that the results based on MMRM model with the MAR assumption is not robust.
5. Repeat Step 2 for the imputed data sets with a shift parameter applied.
6. Repeat Step 3 to obtain the 2-sided 95% CI for the difference between abaloparatide-sMTS and abaloparatide-SC to see if the lower bound of the 95% CI is still  $> -2.0\%$ .
7. Repeat the Steps 4-6 with a more stringent shift parameter applied until the lower bound of the 95% CI  $\leq -2.0\%$ .

Once the NI is established by the primary analysis, the lower bound of the 95% CI should be  $> -2.0\%$ , and the tipping point (TP) that reverses the study conclusion will be determined. The analysis results with the 95% CI from Step 6 will be presented for the shift parameters between  $(TP - 5i)$  and  $\min [0, (TP + 5i)]$ , where  $i$  is the increment of the shift parameter, with a value of 0.01 or less.

Another sensitivity analysis based on the washout imputation method using the observed baseline values will be performed on the primary efficacy endpoint to address the possibility of data missing not at random. The following steps will be followed in this analysis:

1. Calculate the baseline mean and Month 12 standard deviation (SD) of BMD values in each treatment group.
2. Impute the missing BMD values at Month 12 in each arm using a normal random variable with mean and SD respectively equal to the baseline mean and Month 12 SD in that treatment group. A seed value of 940938 will be used at this step.
3. After the missing data imputation for month 12 is completed using the above steps, the percent change from baseline to month 12 will be calculated in each of the imputed datasets.
4. 100 datasets will be generated and will be analyzed using an ANCOVA model with treatment and DXA instrument manufacturer as fixed effects, and the baseline lumbar spine BMD as a covariate for the comparison of percent change of BMD from baseline to Month 12.

5. Treatment effects (difference in LS means between treatments) from these 100 analyses will then be combined using Rubin's Method via SAS PROC MIANALYZE procedure for overall statistical inference.

As a supportive analysis, the primary efficacy endpoint will be analyzed using an ANCOVA model using the last observation carried forward (LOCF) method. The ANCOVA model will include treatment and DXA instrument manufacturer as fixed effects, and baseline lumbar spine BMD as covariate. The LS mean and corresponding 95% CI for the difference between treatment groups (abaloparatide-sMTS minus abaloparatide-SC) at Month 12 will be presented. Missing data imputation based on the LOCF method will be performed as follows:

- a. If baseline BMD is missing, no imputation for post-baseline value will be done and this subject's data will be excluded from the analysis.
- b. If baseline BMD is observed, missing post-baseline BMD will be imputed by the last observed value prior to the missing assessment. That is, if a value is missing at a post-baseline time point, the post-baseline BMD will be imputed using the last value observed at any time (could be a value obtained at an unscheduled visit) between baseline (inclusive) and the specified post-baseline time point.

To investigate the effect of the COVID-19 pandemic, the following sensitivity analyses will also be performed:

- a. MMRM analysis using the nominal visit
- b. MMRM analysis excluding BMD measurements collected outside the allowable time period for data collection. In this analysis, BMD assessments are allocated to a Visit based on the inclusion rules shown in [Table 4](#) below for Sensitivity Analysis b).
- c. MMRM analysis excluding BMD measurements which are more than 30 days after the ideal visit date. In this analysis, BMD assessments are allocated to a Visit based on the inclusion rules shown in [Table 4](#) below for Sensitivity Analysis c).

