## **2. SUBJECT ANALYSIS POPULATIONS**

### **2.1. Population Definitions**

Five subject populations will be considered in the statistical analyses of this study.

- Intention-to-Treat (ITT) population**

The ITT population consists of all subjects randomized into this study.

- Modified Intention-to-Treat (mITT) population**

The mITT population includes all randomized subjects who received at least one dose of study drug and had a baseline lumbar spine BMD measurement and at least one post-baseline lumbar spine BMD measurement.

- Safety population**

The Safety population consists of all randomized subjects who received at least one dose of study drug.

- Per-Protocol (PP) population**

The PP population consists of all mITT subjects who did not have any critical protocol deviations (described in [Section 2.2](#)).

- Antibody Population**

The Antibody population will include subjects in the Safety population who have at least one post-baseline anti-drug antibody assessment.

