#### **4.4.2. Secondary Efficacy Endpoints**

The secondary efficacy endpoints are:

- Percent change from baseline in total hip BMD at 12 months
- Percent change from baseline in femoral neck BMD at 12 months

The secondary efficacy endpoints will be analyzed using the MMRM model similar to the analysis for the primary efficacy endpoint, with the appropriate baseline BMD as covariate for the mITT, ITT, and PP populations. The LS means of the secondary efficacy endpoints for the treatment groups and the treatment differences will be estimated. The corresponding 95% CIs will be presented.

The sensitivity analyses using washout imputation using the observed baseline values described in [Section 4.4.1.2](#) will also be applied to these 2 endpoints.

In addition, sensitivity analyses for addressing the effect of the COVID-19 pandemic and supportive analyses using ANCOVA model with LOCF imputation method, as with the analyses for the primary efficacy endpoint, will also be conducted with the appropriate baseline BMD as covariate. Subgroup analyses using the MMRM model will be performed on the secondary efficacy endpoints using mITT, ITT and PP populations for each of the subgroups defined in [Section 3.8](#). The analyses will use MMRM analysis models as described above. A forest plot of the estimated LS mean (and the corresponding 95% CI) of the difference between the treatment groups will be presented by subgroup for each of the secondary efficacy endpoints.

The analysis of the secondary efficacy endpoints using MMRM model will also be repeated for the Antibody population within each treatment group, in which the subjects who are ADA+ at any post-baseline time point will be compared with subjects who are ADA- at all post-baseline time points, with fixed effects of ADA status (ADA+ vs. ADA-), DXA instrument manufacturer, visit, and ADA status-by-visit, and with the appropriate baseline BMD as a covariate.

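### The washout imputation draws missing Month 12 BMD from arm-level values instead of each woman's own baseline, which inflates the standard error of this sensitivity analysis

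*SAP*

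**What the plan says.** SAP 4.4.1.2 announces that a sensitivity analysis based on the "washout imputation method using the observed baseline values will be performed on the primary efficacy endpoint", to address data missing not at random. The steps are:

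- Step 1 takes each arm's baseline mean and Month 12 SD of BMD values. These are BMD values, not percent changes.
- Step 2 imputes each missing Month 12 BMD "using a normal random variable with mean and SD respectively equal to the baseline mean and Month 12 SD in that treatment group".
- Step 3 says that "the percent change from baseline to month 12 will be calculated in each of the imputed datasets".
- Steps 4 and 5 analyse 100 data sets by ANCOVA (treatment, DXA manufacturer, baseline BMD) and pool them by Rubin's method.

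On populations, the section says: "Additional sensitivity analyses described below will also be performed in the mITT, ITT, and PP populations". SAP 4.4.2 extends the rule to total hip and femoral neck: "The sensitivity analyses using washout imputation using the observed baseline values described in" Section 4.4.1.2 are applied to both.

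**The concern.** The endpoint is a within-subject percent change. A washout scenario supposes that a woman who leaves loses her gain and goes back to where she started. The rule instead gives her a BMD typical of her arm, whatever her own level.

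Take a woman whose baseline is 10% below the arm mean. Her expected imputed change is 100 x (1/0.90 - 1) = +11.1%. For a woman 10% above the mean it is 100 x (1/1.10 - 1) = -9.1%. Neither has been washed out. The spread comes from the rule, not from the missing-data scenario being tested.

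At stake is how this one check is read. A sound non-inferiority result could look fragile because of imputation noise. If dropout is related to baseline BMD, the point estimate could be displaced as well.

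**Working it through.** **The plan's own figure.** From SAP 3.1: margin 2.0, SD 6.35, true difference 0, 426 analysed (213 per arm). The SE is 6.35 x sqrt(2/213) = 0.615. Power from the noncentral t is 0.9003 with 213 per arm and 0.8989 with 212, so 426 reproduces. 426/0.90 = 473.3, hence 474 randomized.

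**Assumptions.** Neither document gives the between-subject BMD CV or the Month 12 missing rate. Assumed here: CV 5, 10 or 15%; 3, 5 or 10% missing per arm; mean gain 10%; change independent of baseline; true difference 0.

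**SD of the imputed percent change.** Let B be the baseline and Y* the drawn value, independent of B. The change is D = 100(Y*/B - 1). To first order, in percentage points squared,

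Var(D) = CV² + (1.10 x CV)² + 6.35².

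The first term comes from the baseline; the other two make up the Month 12 variance.

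| CV | Sum | SD, formula | SD, simulated |
|---|---|---|---|
| 5% | 25 + 30.25 + 40.32 = 95.57 | 9.8 | 9.7 |
| 10% | 100 + 121 + 40.32 = 261.32 | 16.2 | 16.4 |
| 15% | 225 + 272.25 + 40.32 = 537.57 | 23.2 | 24.3 |

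An own-baseline draw gives 6.3.

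**Effect on the standard error.** SAP steps 1-5 were simulated against an own-baseline draw: 213 per arm, 1,000 trials per cell, 100 imputations, ANCOVA with treatment and baseline BMD, Rubin's rules. DXA manufacturer was omitted. Ranges run from CV 5% to CV 15%.

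| Missing per arm | SE as written | SE own-baseline | 95% half-width as written | Half-width own-baseline |
|---|---|---|---|---|
| 3% | 0.66-0.80 | 0.65 | 1.30-1.56 | 1.26 |
| 5% | 0.70-0.92 | 0.67 | 1.37-1.80 | 1.31 |
| 10% | 0.76-1.12 | 0.71 | 1.49-2.19 | 1.39 |

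At CV 15% and 10% missing the half-width exceeds 2.0, so even an observed difference of zero would put the lower bound below -2.0. A second simulation (gain 9%, CV 8-15%, 5-20% missing) gave an SE 1.11 to 1.87 times the own-baseline SE, and above it in every cell.

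**Why the baseline covariate does not help.** Observed women have almost no slope of percent change on baseline, while imputed women have a steep negative one. A single common slope, set mostly by the observed women, cannot absorb it. The simulation includes this covariate.

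**Point estimate, dropout unrelated to baseline.** The mean imputed change is about 100 x CV² (CV as a fraction), that is 0.25, 1.0 and 2.25 points. With equal missingness this cancels: the two rules differ by at most 0.02. With 10% missing on SC and 20% on sMTS (21 and 43 of 213, a gap of 22/213 = 0.103), the difference is about -0.103 x (10 - 0.25) = -1.01, then -0.93 and -0.80. Simulated values are -1.01, -0.93 and -0.78, against -1.04 with own baseline.

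**Point estimate, dropout related to baseline (hypothetical).** Suppose dropouts in both arms have a mean baseline about 0.5 SD below the arm mean. The mean imputed change becomes about +2.7, +6.1 and +10.6% at CV 5, 10 and 15%, where the scenario calls for 0. With equal missingness the difference stays near 0. With 10%/20% missing it is -0.81, -0.50 and -0.11, against -1.04. If only sMTS dropouts are selected this way, at 5-10% missing, the estimate moves toward sMTS by 0.13-0.78 points for low-baseline women and against it by 0.12-0.70 for high-baseline women.

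**The case against.** **No decision hangs on it.** Non-inferiority is judged on the MMRM alone, and the washout is one of several supportive analyses without a success criterion. This stands, and it limits the point to a minor one.

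**Other checks cover the ground.** The tipping-point analysis uses shift parameters "which adjust the imputed values for the abaloparatide-sMTS treatment group" until the lower bound reaches -2.0%. If the result is robust enough, that passes through full loss of gain in sMTS dropouts while SC is left unshifted, which is harsher than a two-arm washout. This is fair, but it does not return dropouts in both arms to baseline. Nor does LOCF in the primary population. It carries forward the last value found "between baseline (inclusive) and the specified post-baseline time point", and every mITT subject "had a baseline lumbar spine BMD measurement and at least one post-baseline lumbar spine BMD measurement". Those missing Month 12 therefore keep an on-study value; own baseline is assigned only to ITT women with no later scan.

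**The comparator is itself conservative.** At 10% missing, the own-baseline draw pooled by Rubin's rules gives an SE of 0.71, while the estimate's empirical SD is 0.55-0.59. For the rule as written the figures are 0.76-1.11 against 0.57-0.78. So the own-baseline draw does not remove all the excess. It still lowers both the SE and the empirical SD, and it removes the dependence on baseline.

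**The size is assumed.** True. At CV 5% the half-widths differ by only 0.04-0.10, and the large figures need CV 10-15% with 5-10% missing. The selection patterns by baseline have no source in the documents. The direction of the SE effect does not depend on these choices.

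**DXA manufacturer was left out of the model.** A check with a manufacturer offset did not reverse the direction, so this affects precision only.

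**Conclusion.** The point holds and is minor. As written, the rule does not carry out a washout to the subject's baseline, and its standard error includes between-subject BMD variance that the scenario does not call for. Confidence is high in the direction and limited in the size. With dropout unrelated to baseline, the SE ranges from barely changed (0.66 against 0.65 at CV 5%, 3% missing) to 1.12/0.71 = 1.58 times too large (CV 15%, 10% missing). In that setting the wider interval works against the product. With baseline-related or unequal dropout the estimate can also shift, sometimes in favour of sMTS.

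The primary MMRM, the tipping-point analysis and the sample size are untouched. The ITT version adds women with no post-baseline scan, so it can only have more values to impute. The same rule is used at total hip and femoral neck, where no size is claimed.

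**What to change.** Replace washout steps 1-2 with: *For each subject missing Month 12 BMD, impute Month 12 BMD = subject's own baseline x (1 + e/100), with e drawn from a normal distribution with mean 0 and SD equal to the observed Month 12 percent-change SD in that arm.* Apply it at lumbar spine, total hip and femoral neck. Keep the seed, the 100 imputations, the ANCOVA and Rubin's rules. Giving washed-out women the on-treatment SD is a choice, and the SAP should state it as one.

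The cost is two sentences of SAP text and a few lines of code, with no new data. The SAP carries September 2021 approvals, so the change needs an amendment before database lock, the date of which is not given. After lock, it would have to be identified in Section 9.8 of the clinical study report, as SAP Section 1 requires for significant changes.
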